12.2.1.2 Causality

Causality defined as the relationship between a study drug and an adverse event assessed according to chronological criteria, pharmacological properties of the drug and a search for other explanations or contributing factors. The causality is to be evaluated initially by the investigator, using the following likelihood scale:

None	Timing incompatible; appearance before study drug introduction, delay before appearance of adverse event too long, or symptoms appeared before event; or due to causes other than study drug administration (e.g. disease, environment etc.).
Unlikely	A clinical event with a temporal relationship to drug administration which makes a causal relationship improbable, and in which other drugs, chemicals or underlying disease provide plausible explanations.
Possible	A clinical event with a reasonable temporal relationship to drug administration, and which could also be explained by concurrent disease or other drugs or chemicals. Information on drug withdrawal may be lacking or unclear.
Probable/Likely	A clinical event occurring in a reasonable temporal relationship to drug administration, unlikely to be due to concurrent disease or other drugs or chemicals. The response to withdrawal (dechallenge) should be clinically reasonable.

It will be specified whether the event is **Serious** or not and if the event is **Critical** or not according to the relevant definition and information regarding **Date of Onset, Date of Resolution, Actions Taken** and **Outcome**.

Ongoing adverse events should be reviewed at each subsequent assessment. If resolved, the details should be recorded in the CRF. If any AE changes for the worse, in frequency of attacks/symptoms or in severity, a new record of the event must be started (i.e. distinct reports are required for differing frequencies and/or severity of the same event to enable comprehensive safety reports and later analysis).

All adverse events, serious or causally related to the treatment or to the research protocol and still evolving at the end of the study are to be followed up until their resolution by the investigator.

12.2.2 Case of Routine Laboratory Measurements

A list of the laboratory normal ranges should be supplied at the start of the study by the implied laboratories or by the investigator to Revimmune.

The results of these will be in the CRF, and if they are abnormal a comment or explanation should be given, where possible using the following categories:

- abnormality not clinically significant (NCS)

- abnormality clinically significant, but normal for the study population (CS/N)
- abnormality clinically significant and is an adverse event (CS/AE)

It should be noted that all clinically significant abnormalities, not normal for the study population, count as Adverse Events even if they are not related to the use of study medication. An Adverse Event Form needs to be completed for all abnormalities falling into this category with all its items and the event must be followed in accordance to the same rules

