
Objectives
	
Primary Objective To study the biological activity and safety of two dosing regimens of CYT107 at 10 µg/kg twice a week for the first week, followed by:
 
 • Once a week for the low frequency regimen • Twice a week for the high frequency regimen • Control group: will receive placebo (NaCl 0.9%) twice a week 
Activity The primary objective is to demonstrate that treatment of lymphopenic septic patients with CYT107 will reverse their low absolute lymphocyte count (ALC) which is a marker of immunosuppression and which correlates with mortality. This primary end point, increased, ALC by >50% in septic patients with lymphopenia, will be measured in the control (placebo) and two “dosing frequency” groups at approximately day 42 following randomization and initiation of study drug treatment.
 
Safety To characterize the short term safety in a context of a single cycle of CYT107 (4 weeks) administered according to these two dosing regimens in lymphopenic sepsis patients. Based on the data collected from previous CYT107 studies in Oncology and HIV infection,(12)(13)(14)(15) treatment of lymphopenic sepsis patients with CYT107 is expected to increase the absolute lymphocyte count (ALC) by greater than 50% from baseline by day 42 after therapy is initiated.
 
To date, CYT107 has not been tested in patients with sepsis. Septic patients frequently have decreased kidney and liver function, changes in circulating blood volume, and loss of vascular integrity with leakage of proteins into the interstitial space.(2) These alterations might impact the pharmacokinetics and pharmacodynamics of CYT107. Thus, we will administer CYT107 using a protocol that is highly similar to a previous protocol that was effective in improving the ALC in patients with cancer, HIV, and hepatitis C and was well tolerated with a low incidence of serious adverse effects.(12)(13)(14)(15)(17).
 
The incidence, type and severity of adverse events occurring during the 6 weeks study period will be analyzed for the control arm and two “dosing frequency” groups.
 
Secondary Objectives To characterize CYT107 pharmacokinetics (PK) in patients with sepsis To characterize CYT107 immunogenicity by detection and quantification of binding antibodies and detection of neutralizing antibodies in positive samples To characterize CTY107 pharmacodynamics, specifically to determine if CYT107 can restore depressed functional activity of immune effector cells in patients with sepsis To determine if CYT107 decreases the incidence of secondary infections in septic patients

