10.2 Data Safety Monitoring Board (DSMB)

The DSMB will be composed of 4 experts who are not involved in the conduct of this trial as investigators but are experienced in the management of Sepsis disease and immunotherapy:

- [name], MD, Brown University School of Medicine, USA
- [name], MD, Vanderbilt University School of Medicine, USA
- [name], PhD, Vanderbilt University School of Medicine, USA
- [name], MD, University of Florida School of Medicine, USA

If need be, the DSMB is free to ask for the advice of one or several other experienced physicians whose name and advice, however, must be communicated to the steering committee.

The mission and rules of DSMB is described in the DSMB charter which will be signed by DSMB member before study initiation.

On an ongoing basis, the DSMB will review:

- All Critical Events.
- All treatment emergent adverse events (TEAEs)
- All SAE assessed by the investigator, by the DSMB, UVEC or by the 3 panel expert committee which adjudicates whether the abnormal finding is secondary to CYT107 or part of the septic process.
- Individual data on the size of lymphoid organs.

The DSMB will review, confirm or discuss the severity grade suggested by the investigator assess the causality relationship to CYT107 and the experimental protocol.

The DSMB will advise the Sponsor regarding study continuation. On an ongoing basis and at the end of the study the DSMB, will review the safety data.

The experts of the DSMB should follow and complete the Causality Assessment Guidelines.

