12.1 Definitions

The following standard definitions for adverse events will be used:

Adverse event: An adverse event is any undesirable or untoward medical event (clinical or non-clinical e.g. abnormal laboratory/EKG/imaging results) which occurs in a patient or in a patient in a clinical trial, who is receiving a pharmacological product, and which is not necessarily causally related to the treatment.

Serious adverse event: A serious adverse event or reaction is any untoward medical occurrence that at any dose:

- results in death
- is life-threatening (the term “life-threatening” in the definition of “serious” refers to an event in which the patient was at risk of death at the time of the event; it does not refer to an event which hypothetically might have caused death if it were more severe.).
- requires inpatient hospitalization or prolongation of existing hospitalization
- results in persistent or significant disability/incapacity
- is a congenital abnormality
- is medically significant (event that may not result in death, be life-threatening, or require hospitalization may be considered serious when, based upon appropriate medical judgment, they may jeopardize the patient or subject and may require medical or surgical intervention to prevent one of the outcomes listed in this definition)

Unexpected Serious Adverse event: An unexpected adverse event is an event, the nature or severity of which is not consistent with CYT107 Investigator's Brochure (updated at least annually).

Critical event: The following events, occurring after the start of CYT107 and considered to be possibly or probably related to the study drug:

- Any grade ≥ 3 Adverse Event (clinical or biological)
- Rash \geq grade 2
- Any diagnosis of lymphoma confirmed by a pathologist
- Any adenopathy compromising or threatening organ function (e.g. mediastinal adenopathy inducing a respiratory distress; inguinal adenopathy inducing an edema of the lower limb; or any adenopathy threatening skin breakdown).
- Splenomegaly that is accompanied by:
 - 1) Clinical hypersplenism
 - 2) Suspicion of a diagnosis of splenic infarct (left upper quadrant pain and imaging study compatible with the diagnosis)
 - 3) Splenic rupture

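### Section 12.2.2 exempts clinically significant laboratory abnormalities from adverse event reporting if they are judged usual in sepsis, with no comparison to the patient's own pre-dose value and in conflict with section 12.1

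*Protocol*

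**What the plan says.** Protocol section 12.2.2 gives three comment codes for abnormal routine laboratory results: not clinically significant (NCS); "abnormality clinically significant, but normal for the study population (CS/N"); and clinically significant and an adverse event (CS/AE). The operative sentence is that "all clinically significant abnormalities, not normal for the study population, count as Adverse Events", whether or not they are related to study drug. It continues: "An Adverse Event Form needs to be completed for all abnormalities falling into this category". Results reach the CRF whatever their code: "The results of these will be in the CRF, and if they are abnormal a comment or explanation should be given".

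Section 12.1 defines an adverse event as "any undesirable or untoward medical event (clinical or non-clinical e.g. abnormal laboratory/EKG/imaging results"). It attaches no test of what is usual in the study population.

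On the population itself, the Synopsis (Objectives) and section 2.4.3.2 both state: "Septic patients frequently have decreased kidney and liver function". Inclusion criterion 4 in section 5.1 requires at least one organ failure.

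On oversight, section 10.2 lists what the DSMB reviews on an ongoing basis: critical events, "All treatment emergent adverse events (TEAEs"), SAEs, and individual data on lymphoid organ size. A later sentence in the same section adds a general review of safety data, both ongoing and at the end of the study.

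**The concern.** Whether a clinically significant result becomes an adverse event depends on how it compares with septic patients in general. The comparison that would separate drug effect from background illness is with the same patient before the first dose, and section 12.2.2 does not ask for it. It gives no threshold, grade, time window or reference range for what counts as usual, so the decision is an individual judgement.

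This population is the one in which such an exemption reaches furthest. Abnormal creatinine, bilirubin, platelets and clotting times are common in septic shock, so a fresh deterioration in any of them can be coded CS/N by someone following the text.

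Safety is part of the primary objective (section 3.1) and of the primary endpoints (section 4.3.1), and section 2.4.3.2 states that the drug has not been tested in sepsis. With about 10 evaluable patients per arm (sections 6.2 and 9.1), a few unrecorded events could change how the adverse event tables read.

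**Working it through.** No figure in the plan is in question, so the check is to follow one result through the documents. Take a clinically significant bilirubin or creatinine result that is worse after dosing than before, does not meet an SAE criterion, and is coded CS/N because such values are common in sepsis.

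| Route | Starts from | Does the CS/N result enter? |
|---|---|---|
| Adverse event form (12.2.2) | CS/AE code | No |
| Causality assessment (12.2.1.2) | Adverse event | No |
| TEAE tables (9.2.5.1) | Adverse event that occurs or worsens on treatment | No |
| Critical event report (12.1, 12.5) | Adverse event of grade 3 or more, possibly or probably related | No |
| Steering Committee review (10.1) | Adverse event of grade 3 or more, or critical event | No |
| DSMB TEAE and critical-event review (10.2) | As above | No |
| CRF entry (12.2.2) | Any result | Yes |
| Laboratory summaries and shift tables (9.2.5.2) | Raw values, changes from baseline | Yes, at analysis |
| DSMB general safety review (10.2); research data reported to committees (4.2) | Safety or research data | Possibly; no laboratory listing, format or timing is given |
| SAE report (12.3) | Seriousness, whatever the cause | Only if the event becomes serious |

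Every route that would give a non-serious result a grade, a causality judgement or an event record starts from the term adverse event, and section 12.2.2 withholds that term.

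The rule also runs against the protocol's own logic elsewhere:

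- In section 12.2.1.2, the Possible category expressly covers events that concurrent disease could also explain. CS/N removes such results before causality is considered.
- Section 9.2.5.1 counts events that worsen on treatment, and section 12.2.1.2 requires a new record when an event worsens. Both look at change within the patient; section 12.2.2 does not.
- Section 10.2 mentions an expert panel that judges whether an abnormal finding comes from the drug or from sepsis, but ties it to SAE review. For non-serious results, that judgement is made by the laboratory code.

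Timing: the laboratory tables are analysis outputs, and the first planned unblinded analysis comes when the last patient reaches day 60 (sections 8.7.3 and 9.3). The SAP describes no adverse event or laboratory safety analysis, so it adds no further route.

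Effect on the comparison between arms: let p1 and p0 be the true proportions with such an event on CYT107 and placebo, and c the fraction coded CS/N, taken as equal across arms because staff are blinded (section 8.7.1).

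- Recorded difference = (1 − c)p1 − (1 − c)p0 = (1 − c)(p1 − p0).
- Recorded ratio = (1 − c)p1 / [(1 − c)p0] = p1/p0.

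So the absolute excess and the event counts shrink by the factor 1 − c, while the ratio is unchanged. The documents give no value for p1, p0 or c, so no numerical loss can be stated.

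**The case against.** The strongest reply is that section 12.2.2 need not be read this way. The codes are comment categories to be used where possible, and nothing says that new worsening after dosing is normal for septic patients. An investigator may code it CS/AE, and section 12.2.1 requires any adverse event to be recorded. Setting aside abnormalities that belong to the disease is also a defensible choice when most patients have them; otherwise the tables fill with background illness.

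A reader might go further than the text allows and infer that sepsis-like toxicity never reaches the adverse event tables or the DSMB, or that monitoring of these organs is switched off. The documents do not support that:

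- Liver, kidney, platelet and clotting tests are scheduled on days 4, 8, 15, 22, 29 and 42 (section 6.3.2).
- The eCRF is due within a week, and the sponsor has read access to review safety data (section 13.1).
- Raw values and shifts from baseline are tabulated regardless of coding (section 9.2.5.2).
- The SAE definition has no population exemption, and SAEs go to the DSMB within 24 hours whatever the cause (sections 12.1 and 12.3).
- The DSMB reviews safety data generally, and its detailed rules are in a charter that is not among these documents (section 10.2).

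All of this stands as a limit on the point. It does not remove it. The permissive reading depends on each coder choosing CS/AE without any instruction to do so. The alternative routes preserve the numbers, but do not give a non-serious result an event record, a grade or a causality assessment.

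**Conclusion.** The point holds as a reporting gap and a conflict between sections 12.1 and 12.2.2. Under the rule as written, non-serious worsening of organ-function tests after dosing can be absent from the TEAE tables, the causality assessment and the DSMB's named TEAE and critical-event streams. It would then be visible only in laboratory summaries and shift tables or through general safety review, unless it became serious.

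Its size is not known. It depends on how often coders would use CS/N for a worsened result, on which the documents are silent. Three limits apply. The critical-event route loses only those results that would have been grade 3 or more and judged possibly or probably related. Under equal coding in all arms the ratio between arms is preserved. The ALC endpoint is unaffected. The conclusion assumes that section 12.2.2 is followed literally and that the DSMB charter does not already require laboratory listings. The Appendix 2 flow chart and the laboratory part of the DAIDS table were not available in the text examined, and nothing is inferred from their absence. This is an inexpensive improvement to a primary safety assessment; it does not show that toxicity would be hidden.

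**What to change.** Change reporting only. Reconcile section 12.2.2 with section 12.1 as follows:

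- Restrict CS/N to clinically significant abnormalities already present before the first dose and not worsened since.
- Take as reference the pre-dose Day 1 value, or the screening value if that is missing. The fallback matters: the pre-dose sampling list in section 6.3.1.1 names ALC, PK and immunogenicity, whereas section 6.1 collects creatinine, liver tests, platelets, PT and PTT at screening.
- Record as an adverse event, grade on DAIDS and assess for causality any clinically significant abnormality that is new, or at least one DAIDS grade worse than that reference.

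It would also help to name laboratory shift tables among the DSMB's inputs in section 10.2.

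The cost is a paragraph in the protocol and in the CRF guidance, using laboratory data already collected. The downside is more adverse event forms and higher reported rates in all arms, including placebo.

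One knock-on must be settled by the sponsor. Section 2.4.3.3 links postponement and suspension of dosing to adverse events, and section 8.6.1 lists a critical event among the grounds for interrupting treatment. Recording more laboratory results as adverse events would bring more of them within those provisions, so these passages must be reconciled with the revised reporting rule. No change to the dosing rules is suggested here.

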12.3 Reporting Serious Adverse Events

All Serious Adverse Events will be reported to the institutional IRB and sent by e-CRF system, e-mail, or fax to the DSMB and Sponsor within 24 hours of being notified of the event using the SAE Report Form (Initial) in the Study Manual, whatever the relationship to the study drug. All information about the adverse event obtained later by the investigator (outcome, more precise medical details, results of investigations, copy of discharge summary etc.) is to be sent as soon as possible to the monitor completing an SAE Report Form (follow-up). When this information is passed on, care must be taken to continue to respect patient anonymity.

The medical monitor from the coordinating site may contact, or visit the investigator, in order to obtain details of the event.

Following collection of information the case should be reviewed separately by the investigator, by Sponsor, by the DSMB. All Serious Adverse Events must be followed by the investigator until resolution or stabilization, and a final assessment sent to Sponsor as a SAE Report Form (follow-up).

In addition, if the investigator becomes aware of the occurrence of an unexpected Serious Adverse Event/ reaction which appears after the end of the study, he or she should inform Sponsor and the institutional IRB following the same procedures described above.

SAEs should be reported to IRB/DSMB and FDA according to institutional and federal regulations.

12.4 Assessment of SAE Expectedness and reference document

The sponsor is responsible of assessing the expectedness of an AE according to the CYT107 Investigator's Brochure (latest version v7) used as the reference document.

12.5 Reporting of Critical Events

All Critical events have to be sent by e-CRF system, e-mail or fax to Sponsor within 24 hours of being notified of the event using the appropriate form (Critical Event report Form).

The medical Monitor may contact, or visit the investigator, in order to obtain details of the event. Following collection of information the case should be reviewed separately by the investigator, by Sponsor and by DSMB.

13.0 Collection and validation of data, and trial monitoring

13.1 Data Collection

Electronic Data Capture (EDC) will be used to collect individual data. An electronic Case Report Form (eCRF) is designed to contain information necessary for the evaluation of the patient and investigational agent. The eCRF must be completed in a timely manner following the visit and no more than a week after. The eCRF must be accurate and complete. All information required by the protocol is to be recorded in the eCRF based on source data. All REDCap data will be made available to the Sponsor in read-only format to review safety data and verify the validity and completeness of the forms.

13.2 Source Data

The investigator and the study nurse coordinator will identify any data that will be recorded directly on the CRF and considered as source data (i.e., no prior written or electronic record of the data). The study coordinator will document this on the study initiation report and revisit and document the use of the CRF as source documents as necessary during the course of the study.

13.4 Data Management/Statistics

Vanderbilt will be functioning as the CRO for the study and it will be responsible for all data management and statistical analysis. The data will be managed through the common database, i.e., Red Cap that is available to all academic centers in the United States.

The clinical data are sent from the clinical sites to the database via a web-based e-CRF and are stored on a server located at the CRO under ORACLE format. Once the clinical data is cleaned and the database is locked, the data will be transferred to SAS for statistical analysis at the CRO in charge of the analysis.

13.5 Quality Assurance

In accordance with local regulations and ICH Good Clinical Practice guidelines, the coordinating center may decide that the clinical trial should be audited in order to examine whether the quality control procedures are sufficiently and correctly adhered to. The audit can take place either at the clinical site or at any other trial drug evaluation site (e.g. laboratory). The investigator will be informed beforehand if an auditor (internal or external) is going to visit.

The local regulations and the ICH Good Clinical Practice guidelines also allow for an inspection by the health authorities. This inspection is similar to an audit but can take place either at the sponsor's or at the investigator's premises.

14.0 Ethical considerations

14.1 Informed Consent

Prior to entering the study, the investigator or designated co-investigator or study nurse, will explain to each patient or, in the case that the patient is not able to sign for himself/herself, their family member or legal authorized representative (LAR) the nature of the study, its purpose, procedures, expected duration, alternative therapy available, and the benefits and risks involved in study participation.

Patients/LAR will be provided a consent document and the opportunity to ask questions; information will be provided regarding voluntary participation and the ability to withdraw at any time from the study without prejudice. After this explanation and before any study-specific procedures have been performed, the patient or LAR will voluntarily sign and date an informed consent document.

The patient/LAR will be provided with a copy of the signed informed consent document. The original document will be maintained in the patient's research file, in accordance with all HIPAA and IRB regulations.

